2. PROTOCOL SYNOPSIS

TITLE	Preventing Cholestasis in Premature Infants Using SMOFLipid®					
OBJECTIVES	
Primary Objective
 
 To compare a mixed parenteral lipid emulsion containing fish oil (SMOFLipid®) with a soybean oil based lipid emulsion (Intralipid®) for its effect on the occurrence of parenteral nutrition associated cholestasis in extremely low birth weight infants 
Secondary Objectives
 
 To assess the impact of SMOFLipid® on the long term neurocognitive development of extreme low birth weight infants at 12 and 24 months of corrected age 					
DESIGN / PHASE	Prospective, randomized, double-blind, phase IV study.					
STUDY PLANNED DURATION	First patient First visit	1st month	Last patient First visit	36 month s	Last patient Last visit	62 months
CENTER(S) / COUNTRY(IES)	Single center, Austria (Medical University Vienna, Austria; Department of Neonatology, Pediatric Intensive Care and Neuropediatrics, University Children's Hospital,)					
PATIENTS / GROUPS	
200 patients in 2 groups 100 patients per group Block randomization ratio 1:1, stratification by sex and weight (in two groups: < 750 gram vs. ≥750 gram).
 
In case of twins, randomization will be applied to the firstborn; the twin will be assigned to the other treatment group. Triplets or higher will be excluded.
					
INCLUSION CRITERIA	
 Infants born with a birth weight ≤ 1000 Gram (= extreme low birth weight infants) Admission to the neonatal ward in the first 24 hours of life Informed consent obtained and randomized on study drug the first 5 days of life 					
EXCLUSION CRITERIA	
 Triplets or higher Conjugated bilirubin > 1.5 mg/dl before inclusion to the study Conditions associated with cholestasis independent of parenteral nutrition: 
 Inborn errors of metabolism Viral Infections (cytomegaly virus, HIV, Hepatitis B, C) Immune mediated hemolytic disease (e.g. Rhesus incompatibility) Cystic fibrosis Primary cholestatic diseases of the liver For Neurodevelopmental outcome in follow up phase: Congenital neurological malformations and chromosomal aberrations 					
STUDY PERIODS	
 Operational Phase: The operational phase of the study will last for three years (months 1-39) and start with the inclusion of the first patient to the trial and will end with the last patient's discharge from hospital. Follow Up: The follow up phase will last start with the first included patient reaching the age of 12 months corrected age and will end at 24 months of corrected gestational age of the last included patient (months 15-62) 					
INVESTIGATIONAL DRUG	SMOFLIPID®:					

	initial dose: 1g/kg/day target dose: 3g/kg/day
COMPARATIVE DRUG /CONTROL CONDITION	INTRALIPID® initial dose: 1g/kg/day target dose: 3g/kg/day
CONCOMITANT MEDICATION	In case of of cholestasis (i.e. conjugated bilirubin two times > 1.5 mg/dl), ursodeoxycolic acid at 20-30 mg/kg/day is the treatment of choice. In case of severe cholestasis (i.e. conjugated bilirubin > 6 mg/dL) and elevation of liver enzymes (3 times over normal) a rescue therapy using pure fish oil (Omegaven®) at 0.5-1 g/kg/day will be allowed.
EFFICACY ENDPOINT	Incidence of parenteral nutrition associated cholestasis (PNAC), defined as conjugated bilirubin > 1.5 mg/dl measured on two consecutive occasions by blood sampling performed at least every 10 +/- 4 days. Based on a present incidence of 25 % using the comparative drug at the study center (unpublished data 2007-9) an absolute difference of 15 % between the groups (25% vs. 10% incidence) was considered clinically significant.
TOLERABILITY / SAFETY ENDPOINTS	-
PHARMACOKINETIC / PHARMACODYNAMIC ENDPOINTS	-
QUALITY OF LIFE / PHARMACOECONOMIC ENDPOINTS	-
STATISTICAL METHODOLOGY	
Primary Endpoint PNAC (definition see efficacy endpoint)
 
Null and alternative hypotheses: H₀ : The percentage of PNAC in group 1 (investigational drug) equals group 2 (comparative drug) H₁: The percentage of PNAC in group 1 (investigational drug) does not equal group 2 (comparative drug)
 
Sample size calculation A sample size estimation using a χ^2-test indicated that 200 infants (100/group) are required to detect a 15% difference (10% in group 1 vs. 25% in group 2) with a power of 80% and a two-sided significance level of 0.05. The estimated drop out rate is 22%. Therefore, a sample size of 122 patients per group is planned. For sample size estimation, data were assumed to be independent.
 
Statistical methodology Main analysis set(s) A χ^2-test will be used for analysis of the primary outcome PNAC. Additionally, the effect of treatment and other relevant influence factors (i. e. duration of parenteral nutrition, birth weight, necrotizing enterocolitis) on the primary endpoint will be analyzed using a logistic regression model with

	
stepwise selection. In case of twins, the analysis will be carried out 1) as mentioned above, but only including the firstborn and 2) by calculating a generalized linear model with mother as random factor.
 
Other endpoints
 
Bailey Scales of Infant Development III at 12 and 24 months: Differences in the scores of psychomotor development and neurocognitive development, respectively, between the groups will be analyzed by repeated measures ANOVAs, also accounting for confounder factors (e.g. birth weight, ...). In case of twins, the analysis will be carried out 1) as mention above, but only including the firstborn and 2) by calculating a mixed model with mother and child as random factor. In case of too many drop outs, descriptive statistics will be carried out.
 
For Gross Motor function measurements at 12 and 24 months, descriptive statistics will be conducted.

--	--

3. LIST OF ABBREVIATIONS

ELBW	Extreme Low Birth Weight
ICH	International Conference on Harmonization
ILE	Intravenous Lipid Emulsion
GCP	Good Clinical Practice
DHA	Docosahexaenoic Acid
DOH	Declaration of Helsinki
LC-PUFA	Long Chain Polyunsaturated Fatty Acids
PN	Parenteral Nutrition
PNAC	Parenteral Nutrition Associated Cholestasis

5. BACKGROUND INFORMATION

5.1 Background

5.1.1 Parenteral nutrition associated cholestasis (PNAC)

Since the first description of parenteral nutrition associated liver disease ¹ it is well established that patients receiving parenteral nutrition (PN) are at risk for developing hepatic complications. In neonates and infants, liver injury is characterized by an early occurrence of intrahepatic cholestasis - i.e. parenteral nutrition associated cholestasis (PNAC) - characterized by a rise in serum conjugated bilirubin ². In severe cases liver cell damage and even progressive liver dysfunction with an incidence of hepatic failure of up to 17 % is described ³.

5.1.2. Extreme low birth weight infants

Preterm infants with extreme low birth weight (ELBW) < 1000 gram are often dependent on long term PN due to intolerance of enteral feedings ⁴. Additionally they frequently acquire nosocomial infections and are at risk for developing necrotizing enterocolitis, a severe inflammatory disease of the intestine with considerable long term morbidity such as short gut syndrome. Prematurity, long term PN, nosocomial infections, necrotizing enterocolitis and short gut syndrome are all risk factors for the development of PNAC. Therefore ELBW infants are at high risk to develop this complication ².

5.1.3. Parenteral lipids as pathogenic factor in PNAC

Besides factors related to prematurity and its complications or short gut syndrome, PNAC is - as already proposed by the condition's name - closely linked to aspects of PN. Hypercaloric feeds with an excess of glucose can result in chronic cholestasis ⁵. Most important however, intravenous lipid emulsions (ILE) seem to be implicated in the development of PNAC. Higher parenteral lipid administration has been documented to be correlated with cholestasis in pediatric patients ⁶ as well as very low birth weight infants ⁷.

5.1.4. Soybean oil based intravenous lipid emulsions

Until nowadays, standard of care for supplying lipids in PN of preterm infants and sick neonates are ILE based on soybean oil (Intralipid®) ². Some of the components of soybean oil are believed to be implicated in the pathogenesis of PNAC. Their high content of ω -6 polyunsaturated long chain fatty

acids may exert pro-inflammatory effects and plant sterols from soy may reduce bile flow and both factors were linked to the development of PNAC⁸.

5.1.5. Fish oil based intravenous lipid emulsions

In recent years, ILEs containing fish oil were proposed for treatment of PNAC in pediatric patients mainly suffering from short gut syndrome. Two research groups consecutively described the successful treatment of severe PNAC in neonates using Omegaven®^{9,10} an ILE composed exclusively of fish oil. The rationale behind the positive effects observed is built on their high content of ω -3 fatty acids which act anti-inflammatory and are thought to improve bile flow¹¹. However, whether fish oil or only replacement of soybean oil based ILE in PN⁶ caused the improvement in these patients, cannot be concluded. Prospective trials are required to substantiate the evidence⁸.

5.1.6. Preventing PNAC in ELBW infants

In view of their high risk to develop PNAC, ELBW infants could profit from a prophylactic intervention. Based on the promising results in the treatment of PNAC, ILEs based on fish oil seem attractive candidates. However, an ILE based on 100% fish oil like Omegaven® may deliver not enough ω -6 fatty acids and therefore cannot be used as the exclusive ILEs for nutrition of ELBW infants⁸.

With a broader panel of ILEs available today, a mixture of fishoil with soybean oil, medium chain triglycerides and olive oil (SMOFLipid®) has recently emerged. A prospective study in a total of 60 preterm infants showed that PN with SMOFLipid® induced lower serum γ -glutamyl transferase levels compared to controls receiving a soybean oil based ILE, suggesting a favourable influence on cholestasis and liver function¹². A prospective randomized trial in 28 pediatric patients demonstrated a reduction in total bilirubin levels using SMOFLipid® compared to a soybean oil based ILE¹³. Importantly SMOFLipid® is registered for PN of preterm infants, which makes a direct comparison of Intralipid® and SMOFLipid® in these vulnerable patients ethically acceptable¹⁴.

5.1.7. Fish oil and neurocognitive development

Long Chain polyunsaturated fatty acids (LC-PUFA) are both structural and functional lipids playing an important role in growth and development of the fetus and the newborn. In particular the 22:6 ω 3-LC-PUFA docosahexaenoic acid (DHA) is deemed to be crucial for a normal development of the fetal brain. *In utero*, high amounts of DHA cross the placenta in the last trimester. After birth mother's milk is the most important source¹⁵.

Preterm infants – as their endogenous capacity to synthesize DHA from precursor fatty acids is limited – depend on exogenous supply¹⁶. In this context, preterm infants accumulate a deficit of up

to 44% compared to *in utero* accretion rates¹⁶. In view of the documented correlation of DHA deficit and low birth weight¹⁶ ELBW infants are at particular risk, as they depend PN for several weeks and DHA is absent in the traditional soybean oil based ILEs. As the only source of DHA for the preterm infant is mother's milk or preterm formula and not ILEs, the prolonged time until full enteral feeds are established in these patients seems particularly critical.

Therefore an ILE like SMOFLipid® containing fish oil that provides DHA would reduce this deficit and may therefore confer potential benefits for the neurocognitive development.

5.1.8. Current Status of research on fish oil and parenteral nutrition associated cholestasis in preterm infants

There are currently no studies published on a fish oil containing ILE for prophylaxis of PNAC.

There is growing supportive evidence for treatment of established PNAC using ILE based on fish oil in pediatric patients from two observational and one prospective clinical trial, but there are no data from preterm infants.

The growing belief in a therapeutic effect of fish oil containing ILEs on PNAC is based on the published experience of clinicians from Boston around Mark Puder¹¹ and Toronto around Paul Wales⁹. They both described neonates with severe short gut syndrome and PNAC that dramatically improved after replacing some of the 100% soybean oil based ILE "Intralipid®" with a 100% fish-oil based ILE (Omegaven®) (Toronto) or completely switching over to a fish oil based ILE (Boston). The Boston group reported a resolution of cholestasis in 45-61 % (published cases: 60)^{10,17}. The Toronto group reported a rate of resolution of 63% (published cases: 22)¹⁸. Pooling these cases together, a mean of 53.6 % (44/82) of patients showed reversal of cholestasis. For comparison, historical cohorts of comparable patients who received the soybean oil based Intralipid® for PN, showed resolution of cholestasis only in 5-33 % during the disease course (published cases: 47)^{10,17}.

The only prospective trial using a mixed ILE containing fish oil (SMOFLipid®) in pediatric patients reported a significant reduction of total bilirubin levels compared with the soybean oil based ILE Intralipid®¹³.

The only prospective study performed in a population of preterm infants was performed by Tomsits et al¹². In healthy preterm infants (birth weights 1000 – 2500 gramm) they demonstrated good clinical tolerance and lower γ -glutamyl transferase levels using SMOFLipid® compared to standard care with Intralipid®. Though liver function was only a secondary outcome parameter of the study and the observational period was too short to assess any effect on PNAC, this finding supports a prophylactic effect of SMOFLipid® on liver function, underlining the need for further investigations.

5.1.9. Current Status of research on fish oil and neurodevelopment of preterm infants

There are currently no studies on long term neurodevelopment of preterm – in particular ELBW - infants after using a fish oil containing ILE.

There are prospective trials on enteral supplementation with LC-PUFA containing DHA from fish oil in preterm infants and during pregnancy with mixed results ^{15,19}.

Clinical studies in preterm infants focused on enteral supplementation of LC-PUFAs (including DHA) from fish oil in formula feedings. In this context, a Cochrane Review in 2008 by Simmer et. al ¹⁹ concluded that currently there is no convincing evidence of a sustained improvement of neurodevelopment by LC-PUFA supplementation. However, as the mean birth weight of preterm infants enrolled in these studies was consistently > 1000 gram (1074 – 1980) the authors stressed that ELBW infants should be investigated ¹⁹. In this context, there is indirect evidence from two prospective randomized trials, that supplementation of pregnant women with fish oil converts a beneficial effect on later neurodevelopment of their children ¹⁵. In line with the evidence from these trials, using an ILE containing fish oil for parenteral nutrition of ELBW infants could close the gap until ELBW infants are fully nourished with mother's milk or formula (supplemented with LC-PUFA). A reduction of the DHA deficit these infants normally accumulate ¹⁶ may confer a benefit to neurodevelopment.

5.2 Study rationale

Primary endpoint:

ELBW infants are at high risk for development of parenteral nutrition associated cholestasis (PNAC). There is growing evidence for a positive effect of fish oil based intravenous lipid emulsions (ILE) for the treatment of PNAC. Primary use of a fish oil containing ILE for PN may prevent the development of PNAC.

Secondary Endpoint:

ELBW infants accumulate a deficit of ω 3-LC-PUFA (especially DHA), which are important for neurodevelopment. An ILE containing fish oil provides these fatty acids and would reduce the deficit in ELBW infants, which may improve their neurocognitive development.

6. STUDY OBJECTIVES

6.1 Primary Objective

To investigate whether ELBW infants treated with two different ILEs (investigational drug: SMOFLipid®, comparative drug: Intralipid®) differ in the occurrence of PNAC (conjugated bilirubin > 1.5 mg/dl, measured on two consecutive occasions).

6.2 Secondary Objectives

To investigate whether ELBW infants treated with two different ILEs (investigational drug: SMOFLipid®, comparative drug: Intralipid®) differ in their neurodevelopment (Bailey Scales of Infant Development III) at 12 and 24 months of corrected gestational age

7. STUDY DESIGN

7.1 Study population

7.1.1 Subject population

Population: Extreme low birth weight (ELBW) infants

Recruitment: About 90 ELBW infants are admitted to our unit each year in the first 24 hours of life.

We expect to recruit 90 % (81 patients/a year) to the study.

Drop Outs: Based on a mortality of 22% in 2010 ([name], unpublished data) and a conservative calculation, we expect 18/81 patients to drop out, leaving 63 patients a year for analysis of the primary outcome. We do not expect any other reasons for drop out.

Losses to follow up: 63 patients are expected to be discharged from hospital each year. Based on a follow up rate of 60% after discharge in 2009 ([name], unpublished data), we expect about 38/63 patients to be available for analysis of the secondary outcome each year. In the end we expect to lose 80/200 patients to follow up.

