7.1.5 Withdrawal and replacement of subjects

Criteria for withdrawal

Premature discontinuation from the study is to be understood when the subject did not undergo End of Study (EOS) examination and / or all pivotal assessments during the study.

Subjects must be withdrawn under the following circumstances:

- at their parent's request at any time
- if the investigator feels it would not be in the best interest of the subject to continue
- if the subject violates conditions laid out in the consent form / information sheet or disregards instructions by the study personal
- if the subject is transferred to another hospital before parenteral nutrition is discontinued
- if the study drug was not provided < 80% of time as planned per protocol
- If an exclusion criterion is met, after inclusion to the study (except neurological malformation and chromosomal aberration which only leads to withdrawal from follow up analysis except screening for adverse events)
- death before day of life 28

In all cases, the reason why subjects are withdrawn must be recorded in detail in the CRF and in the subject's medical records. Should the study be discontinued prematurely, all study materials (complete, partially completed and empty CRFs) will be retained.

Follow-up of patients withdrawn from the study

In case of premature discontinuation after study drug intake, the investigations scheduled for the EOS visit will be performed 7 +/-4 days after study drug discontinuation. The subjects will be advised that participation in these investigations is voluntary. Furthermore, they may request that from the time point of withdrawal no more data will be recorded and that all biological samples collected in the course of the study will be destroyed.

Replacement policy

Patients withdrawn from the study < 28 days (outcome cannot be calculated) will be replaced and the next free subject number will be allocated. Drops outs will be included in the sample size. If patients are withdrawn from the study and the outcome can be calculated, (more than two blood samples taken), they will be considered in the intention to treat analysis (see chapter 10)

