8.2 Randomization and stratification

On day 0, patients are randomized to one of the two study groups and the study medication is provided. Study subjects will be block randomized (ratio 1:1) and stratified according to sex and birth weight (in two groups: < 750 gram vs. ≥ 750 gram) using an online randomization programme provided by the Center for Medical Statistics, Informatics, and Intelligent Systems of the Medical University of Vienna. In case of twins, randomization will be applied to the firstborn; the twin will be assigned to the other treatment group.

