8.5.4 Laboratory Tests

Blood counts and complete blood chemistry is routinely performed according to the local standard of care at the unit at least every 10 +/-4 days until discharge from hospital. No additional blood sampling or analyses will be performed in study subjects in comparison to standard of care of ELBW infants.

All laboratory parameters of interest for the study routinely performed are:

denomination	Variable	time of measurement
Conjugated bilirubin	mg/dL	every 7-14d until discharge
ALAT	U/L	every 7-14d until discharge
ASAT	U/L	every 7-14d until discharge
γ-glutamyltransferase	U/L	every 7-14d until discharge
Alkaline phosphatase	U/L	every 7-14d until discharge
Triglycerides	mg/dL	every 7-14d until discharge

Additional parameters used for the study

All additional parameters of interest are documented or produced routinely during the patient's admission to the unit or follow-up according to the local standard of care. No additional interventions will need to be performed.

denomination	Variable	time of measurement
Basic demographic data		
Sex	m/f	at birth
Gestational age	days	at birth
Twin	yes/no	at birth
Mode of delivery	caesarean/spontaneous	at birth

Prenatal steroids for lung maturation	yes/no	at birth
Birth weight	gram, Z Score	at birth
Birth crown heel length	cm, Z Score	at birth
Birth head circumference	cm, Z Score	at birth
Small for gestational age	yes/no	at birth
Apgar scores at 1, 5 and 10 minutes	0-10	at birth
Umbilical artery pH at birth	range 6.7 – 7.6	at birth

Growth and nutrition parameters

Time on parenteral nutrition	days	at discharge
Total amount of parenteral lipids	gram	at discharge
Enteral nutrition in 1 st first week of life	ml/day	day 0-6
Weight at discharge	gram, Z Score	at discharge from hospital
Crown heel length at discharge	gram, Z Score	at discharge from hospital
Head circumference at discharge	gram, Z Score	at discharge from hospital
Death > 28 days	yes/no	day of life 28 - discharge
(Death before 28 days = drop out)		
If death	day of life	day of life 28 - discharge

Neonatal (preterm) morbidities

Intraventricular hemorrhage Grad 3/4	yes/no	at discharge
Cystic periventricular leucomalacia	yes/no	at discharge
Chronic lung disease	yes/no	at discharge
Received steroids for chronic lung disease	yes/no	at discharge
Treatment for pulmonary hypertension (Sildenafil, iNO)	yes/no	at discharge
Culture proven sepsis	yes/no	at discharge
Necrotizing enterocolitis Bell's Stage ≥ IIa	yes/no	at discharge

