11.2 Sample size considerations

Data investigating the incidence of PNAC in our unit showed an incidence of 25 % from 2007-9 (unpublished data). We considered a difference of 15% between the groups (incidence of PNAC: 25% for Intralipid and 10% for SMOFLipid, respectively) as a clinically relevant effect. A sample size estimation based on a χ^2 -test indicated that 200 infants (100/group) are required to detect a difference of 15% between the groups with a power of 80% and a significance level of 0.05. The estimated drop out rate is 22%. Therefore, a sample size of 122 patients per group is planned. For sample size estimation, data were assumed to be independent.

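### The 22% drop-out allowance is mortality alone and does not match the plan's own drop-out and withdrawal rules; even at 22%, 122 per group leaves about 95 evaluable (78% power), not 100

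*Combined protocol and SAP*

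**What the plan says.** - **Basis of the rate (7.1.1).** About 81 infants a year are expected to be recruited. Mortality of 22% in 2010, described as a conservative basis, gives 18 of 81 drop-outs and leaves 63 a year for the primary outcome. The section then states: "We do not expect any other reasons for drop out". The same 63 are also taken as the number discharged from hospital.
- **Use of the rate (11.2).** With "incidence of PNAC: 25% for Intralipid and 10% for SMOFLipid, respectively", the section says "200 infants (100/group) are required to detect a difference of 15% between the groups". It continues "The estimated drop out rate is 22" per cent and plans 122 per group. The synopsis gives the same calculation, "with a power of 80% and a two-sided significance level of 0.05".
- **What counts as drop-out (8.5.4 and 7.1.5).** The parameter list in 8.5.4 has "Death before 28 days = drop out" and records deaths from day 28 to discharge as data. Section 7.1.5 likewise lists only death before day 28 as a withdrawal.
- **Other mandatory withdrawals (7.1.5).** These include parental request, investigator judgement, an 80% exposure rule, an exclusion criterion met after inclusion, and "if the subject is transferred to another hospital before parenteral nutrition is discontinued".
- **Rules that limit the loss.** Sections 7.1.5, 11.1 and 11.5 keep a withdrawn infant in the (modified) intention-to-treat analysis if more than two blood samples were taken. Section 7.1.5 replaces infants withdrawn before day 28 whose outcome cannot be calculated. It then says that drop-outs are counted within the sample size.

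**The concern.** The allowance should estimate how many randomised infants will have no usable primary outcome. The 22% is a different quantity in two respects. It carries no day-28 limit, and because the same 63 infants are both analysable and discharged, it works as mortality to discharge; the plan's drop-out is death before day 28. It also sets every non-death loss to zero, although 7.1.5 names several reasons for which an infant must be withdrawn, and parenteral nutrition lasts a mean of 44 days (SD 34, section 7.1.4).

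At stake is whether the plan delivers the 100 evaluable infants per group to which its 80% power is tied. The per-protocol set is more exposed: section 11.1 requires the full 18 weeks and study drug as planned, so most mandated withdrawals would leave it. Section 11.5 calls for per-protocol analysis, and no section names one set as primary for the chi-square test.

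**Working it through.** **Inputs.** 25% versus 10%, two-sided 0.05, 80% power, 100 per group evaluable, 22% drop-out, 122 per group planned (synopsis and 11.2); 1:1 allocation (8.2); 81 recruited and 63 analysable a year (7.1.1); last patient's first visit at 36 months (synopsis).

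**1. Reproduce the plan's figure.** Chi-square test with pooled variance under the null and no continuity correction. The mean rate is 0.175.

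n = [1.960 x sqrt(2 x 0.175 x 0.825) + 0.842 x sqrt(0.25 x 0.75 + 0.10 x 0.90)]² / 0.15²
= [1.960 x 0.5374 + 0.842 x 0.5268]² / 0.0225
= (1.0532 + 0.4434)² / 0.0225 = 99.5, so 100 per group.

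Power at n per group is Φ[(0.15 x sqrt(n) − 1.0532) / 0.5268]. At n = 100 this is Φ(0.848) = 80.2%. The plan's figure is confirmed.

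**2. Check the inflation.** 100 x 1.22 = 122, which is the stated number. To have 100 left after losing 22%, one needs 100 / (1 − 0.22) = 128.2, rounded up to 129.

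**3. Apply the plan's own 22% to 122, without replacement.** 122 x 0.78 = 95.2 per group. Power = Φ[(0.15 x 9.755 − 1.0532) / 0.5268] = Φ(0.778) = 78.2%. With 122 enrolled, 100 remain only if the total loss is at most 1 − 100/122 = 18.0%.

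**4. Cross-check with the recruitment forecast.** 3 x 81 = 243, close to 2 x 122 = 244. 3 x 63 = 189, not 200. That is 94.5 per group, for which the same formula gives 77.9%.

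**5. Direction of the remaining mismatch.**

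| Feature of the plan | Effect on the evaluable number (modified intention-to-treat) |
|---|---|
| Deaths from day 28 on are included in the 22% but are not drop-outs | True loss smaller than 22% |
| Non-death withdrawals set to zero | True loss larger, but only for infants without a calculable outcome |
| Infants with more than two samples are kept | Limits the loss from withdrawal |
| Withdrawals before day 28 without an outcome are replaced | Limits or removes early loss, including early deaths |
| Drop-outs are counted within the sample size | Appears to limit replacement; how the two combine is not stated |

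The documents give neither the split of deaths at day 28 nor a rate for any other withdrawal. If every infant without an outcome were replaced on top of 122, the evaluable number would approach 122 and power 87.4%. With no replacement and 22% loss it is 78.2%. The text does not say which applies.

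**The case against.** The strongest reply is that withdrawal is not loss. Table 1 schedules liver tests at randomisation, week 2 and week 4, so an infant withdrawn after about day 28 would usually have three samples and stay in the modified intention-to-treat set. Earlier withdrawals without an outcome are replaced. A list of withdrawal reasons says what happens if an event occurs and is not a forecast that it will. Late deaths make 22% generous, and 7.1.1 calls its calculation conservative.

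Most of this stands, and it rules out a stronger reading. A reader might infer that a further 5, 10 or 15 points of loss cut power to 75.4%, 72.4% or 69.0%. Those values follow from 122 x (1 − 0.22 − extra), but the extra rates are assumptions with no source in the documents. The formula also leaves out replacement and removes infants whom the modified intention-to-treat set keeps. At most they are a sensitivity range under those conditions. A reader might also infer that the 80% claim itself is wrong. It is not: it is tied to 100 evaluable infants per group and reproduces.

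The reply does not remove the whole point. If the baseline sample is not counted and sampling runs every 7 to 14 days (8.5.4), the third sample falls between days 21 and 42, so some infants could leave after day 28 with no outcome and no replacement. Replacement does not protect the per-protocol set against later withdrawals. Nor does anything in the reply explain why an allowance for death before day 28 is filled with mortality that has no such limit.

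**Conclusion.** The point holds in a limited form. The 22% is not an estimate of the loss defined by the plan's rules, and the statement that no other loss is expected has no stated basis beside 7.1.5. Whether 22% is too high or too low cannot be settled from the documents, so a power shortfall in the modified intention-to-treat set due to the make-up of the allowance is not shown.

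The shortfall that can be computed is small and has a different cause. Multiplying by 1.22 instead of dividing by 0.78 leaves about 95 per group and 78.2% power, 1.8 points below the stated 80%. This assumes 22% loss, no replacement, the pooled chi-square test and the planned 25% and 10% rates. The forecast of 189 analysable infants over three years points the same way. For the per-protocol set the loss is probably larger, but the documents give no rate from which to compute it.

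**What to change.** 1. In 7.1.1, delete "We do not expect any other reasons for drop out".
2. In 7.1.1 and 11.2, replace the single mortality figure with an allowance built by component from the unit's records: deaths between randomisation and day 28, and non-death losses (transfer, parental withdrawal, exposure, late exclusion) that occur before the outcome can be calculated.
3. In 7.1.5 and 11.2, reconcile three statements: early withdrawals are replaced, drop-outs are counted within the sample size, and the sample size is already inflated for drop-out. State whether replacements come on top of 122 per group or within it.
4. In the synopsis and 11.2, restate the expected evaluable number and power for the modified intention-to-treat set. If 22% is kept without replacement, this is about 95 per group and 78%. Bring the 63 a year in 7.1.1 into line with it.
5. Give the expected per-protocol number separately.

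The cost is a review of existing unit records and restated text. No additional patients are asked for. If 22% is kept without replacement, the stated power falls by about two points; with a rebuilt allowance it may move either way.
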